#### Dose Reduction Schedule for Acalabrutinib

Starting dose (mg/day)	Dose reduction 1 (mg/day)
200 (100 mg BID)	100 (100 mg QD)

Dose reductions below 100 mg/day are not permitted.

### **Non-hematological grade 3 or higher toxicities**

- For Grade 3 possible or probable acalabrutinib-related non-hematologic toxicities (other than the adverse events specifically described in this section), therapy (acalabrutinib and R-ICE) is to be held for a maximum of 1 week (and d28 of a cycle) until the toxicity returns to Grade 1 or less. If grade 2 during the first cycle, this will be considered a DLT.
- For any Grade 4 non-hematologic toxicity attributed to acalabrutinib, discontinue acalabrutinib and chemotherapy for all remaining cycles; subject is discontinued from study treatment and must complete protocol-specified AE reporting along with follow-up for ongoing SAEs to resolution unless the subject is lost to follow-up.
- If Grade 3 toxicity returns to Grade 1 or less by Day 28, then proceed with next cycle of therapy with acalabrutinib reduced to the next lower dose level.

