### 3.8 DOSING DELAYS AND MODIFICATIONS

#### Treatment modifications

Treatment-emergent adverse events of R-ICE therapy predominantly comprise of hemato-toxicities (such as neutropenia, leukopenia, thrombocytopenia, and anemia). Nonhematologic disorders include asthenia, sensory disturbance, mucositis, alopecia, sepsis, dyspnea, back pain, hyperglycemia, hypersensitivity, and cardiac disorders. Tumor lysis syndrome will be managed as per institutional guidelines. Renal and hepatic adverse reactions will be managed as per institutional guidelines. Treatment modifications are not permitted for R-ICE.

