Based on the specific adverse event observed, 1 dose level reduction is permitted for acalabrutinib (see Table below). If acalabrutinib is withheld for  $\leq$  1 week due to acalabrutinib-related toxicity; study drug should be resumed with a dose reduction when treatment resumes following recovery from the toxicity. If there is unacceptable toxicity despite 1 dose reduction the treatment should be discontinued. If treatment must be withheld for an acalabrutinib-related adverse event that fails to resolve to an acceptable level (eg,  $\leq$  Grade 1 nonhematologic toxicity) within 1 week after the date acalabrutinib was withheld, treatment with acalabrutinib should be permanently discontinued. In this event, the subject will be discontinued from the treatment, and End-of-Treatment Visit assessments will be performed including through the protocol-specified AE reporting window and have follow-up for ongoing SAEs to resolution or stability unless the subject lost to follow-up. (see section 6.2.6)

Acalabrutinib dose adjustments also apply to cycle 1.

**Acalabrutinib** dose will not be reduced for hematological toxicities unless the hematologic toxicities fail to recover by day 21 of a cycle.

The actions in the table below should be taken for the following toxicities at day 21 of the cycle:

- Grade 4 ANC (<500/ $\mu$ L) for  $>7$  days
- Grade 3 thrombocytopenia (<50,000/mcL) in the presence of clinically significant bleeding events
- Grade 4 thrombocytopenia (<25,000/mcL)
- Grade 3 or 4 nausea, vomiting, or diarrhea, if persistent, despite optimal antiemetic and/or anti-diarrheal therapy
- Any other Grade 4 or unmanageable Grade 3 toxicity.

For Grade 3 or 4 atrial fibrillation or persistent atrial fibrillation of any grade, consider the risks and benefits of acalabrutinib treatment. *If clinically indicated, the use of anticoagulants or antiplatelet agents may be considered for the thromboprophylaxis of atrial fibrillation.*

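### Section 3.8 gives incompatible actions for Grade 4 non-hematologic toxicity attributed to acalabrutinib; separately, Appendix 1 footnote d disagrees with the creatinine criterion

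*Combined protocol and SAP*

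**What the plan says.** All of the following are in Section 3.8 unless another place is named.

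- **Stop rule** (Non-hematological grade 3 or higher toxicities, second bullet): "For any Grade 4 non-hematologic toxicity attributed to acalabrutinib, discontinue acalabrutinib and chemotherapy for all remaining cycles". The first bullet, on Grade 3, excepts events described elsewhere in the section. The Grade 4 bullet carries no such exception.
- **Resume sentence** (text following the DLT list): after a hold of 1 week or less for acalabrutinib-related toxicity, study drug should restart at a reduced dose once the patient has recovered. No grade limit is given. If a related event has not settled to an acceptable level (for example Grade 1 or less) within 1 week of withholding, acalabrutinib ends permanently.
- **Day-21 list** (same text): "The actions in the table below should be taken for the following toxicities at day 21 of the cycle". The list includes "Grade 3 or 4 nausea, vomiting, or diarrhea, if persistent, despite optimal antiemetic and/or anti-diarrheal therapy" and "Any other Grade 4 or unmanageable Grade 3 toxicity".
- **The table** (Dose Reduction Schedule): one step, 100 mg BID to 100 mg QD, with "Dose reductions below 100 mg/day are not permitted". A related sentence reads "If there is unacceptable toxicity despite 1 dose reduction the treatment should be discontinued". R-ICE is not adjusted: "Treatment modifications are not permitted for R-ICE".
- **Atrial fibrillation**: "For Grade 3 or 4 atrial fibrillation or persistent atrial fibrillation of any grade, consider the risks and benefits of acalabrutinib treatment".
- **DLT text**: related Grade 4 non-hematologic toxicity is a DLT, and a patient with a DLT is allowed to stay on treatment at a lower acalabrutinib dose.
- **Hepatic impairment**: after severe impairment, drug is held and re-treatment is allowed on improvement, whether or not the event is attributed to acalabrutinib.

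On creatinine, criterion 7e-f in Section 3.3.1 and the synopsis accept a normal value, or clearance of at least 40 mL/min/1.73 m² when creatinine is above normal. Appendix 1 footnote d asks for a calculated clearance of at least 60.

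**The concern.** The same event meets two mandatory instructions. One ends both acalabrutinib and R-ICE. The other puts the patient back on acalabrutinib at half the daily dose with R-ICE unchanged. Section 3.8 itself notes that this combination has had no phase I study, and three centers will apply the text. Two centers following the protocol in good faith could therefore treat the same patient differently, and one of them would re-expose the patient to a drug held responsible for a life-threatening event.

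The choice also decides how many R-ICE cycles the patient has received when response is assessed. Section 5.2.1 sets the primary endpoint as the CR rate at the end of cycle 3.

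The footnote carries a different risk: a site that screens from the Appendix 1 schedule could turn away a patient who meets the inclusion criteria.

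**Working it through.** This is a comparison of text. The plan has no figure to reproduce on this point, and only simple counting is needed.

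**Step 1. Which rules reach an attributed Grade 4 non-hematologic event?**

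| Rule in 3.8 | Action | Force | Limited by attribution, grade or day? |
|---|---|---|---|
| Grade 4 bullet | Stop acalabrutinib and R-ICE | Mandatory | Attributed, Grade 4, any day |
| Resume sentence | Restart at lower dose after a hold of 1 week or less | Should | Related; no grade or day limit |
| Day-21 list and table | 100 mg BID to 100 mg QD | Should | Grade 4 GI (persistent) or other Grade 4; day 21; attribution not mentioned |
| Atrial fibrillation line | Weigh risks and benefits | Permissive | Includes Grade 4 |
| DLT line | Continuing at lower dose allowed | Permissive | Related Grade 3 or 4 in cycle 1 |
| Hepatic re-treatment | Hold, then re-treatment allowed | Permissive as to re-treatment | Severe impairment; attribution not mentioned |

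The first row is incompatible with the second and third. The last three rows can be obeyed while also obeying the first, so they add ambiguity and not contradiction. The Cycle delay criterion for starting a new cycle covers non-hematologic toxicity of grade 3 and above, so it does not exclude retreatment after a recovered Grade 4 event.

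**Step 2. When do the actions differ?** All of these must hold:

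- The event is attributed to acalabrutinib; otherwise the stop rule does not apply.
- It occurs in cycle 1 or 2, because no cycle follows cycle 3.
- The patient is on 100 mg BID, since no dose below 100 mg per day is allowed.
- It resolves within 1 week of withholding (resume text) and by day 28 of the cycle (Cycle delay).

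If the dose or resolution condition fails, both routes end acalabrutinib.

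**Step 3. Size.** Planned cycles = 3, with acalabrutinib on days 1-21 of each (synopsis). For an event at day 21 of cycle k, counting cycle k's R-ICE as given, the stop rule delivers k cycles and the reduction route delivers 3 at best. The difference is 3 − k cycles and up to 21 × (3 − k) acalabrutinib days.

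| k | R-ICE cycles, stop rule | R-ICE cycles, reduction (best case) | Difference | Further acalabrutinib days (at most) |
|---|---|---|---|---|
| 1 | 1 | 3 | 3 − 1 = 2 | 21 × 2 = 42 |
| 2 | 2 | 3 | 3 − 2 = 1 | 21 × 1 = 21 |
| 3 | 3 | 3 | 3 − 3 = 0 | 21 × 0 = 0 |

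**Step 4. Hold limits.** The resume text, and the first bullet on non-hematologic toxicity, cap a hold at 1 week. The third bullet allows the next cycle if a Grade 3 event recovers by day 28. For a hold starting on day d, the week ends on day d + 7. The third bullet read alone is therefore looser whenever d + 7 < 28, that is, d < 21. Section 3.11 cites Section 3.8 for a limit of more than 28 days of toxicity, and 3.8 contains no such limit.

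**Step 5. Creatinine.** Two groups meet 7e-f but fail footnote d: raised creatinine with clearance from 40 to below 60 (via 7f), and normal creatinine with clearance below 60 (via 7e).

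**The case against.** The strongest reply is timing. The stop rule acts when the event occurs, whereas the list acts at day 21, and gastrointestinal toxicity described as persistent at day 21 must have begun earlier. Such a patient would already be off both treatments, which leaves the list to cover unattributed Grade 4, hematologic and unmanageable Grade 3 events. This is a sensible way to reconcile the text, but the protocol does not state it. It also does not deal with the resume sentence, which concerns acalabrutinib-related toxicity and has no day or grade limit. One could read that sentence as setting only the dose on restart; even so, it treats restart as available and does not exclude Grade 4. Nor does specificity settle the matter: the stop rule is specific to attribution, the gastrointestinal line to event type.

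A reader might infer that the atrial fibrillation and DLT lines contradict the stop rule too. They do not. Both are permissive, and a site that stops treatment breaches neither.

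A reader might also infer that the reduction route always yields two more cycles after a cycle 1 event. It does not. Grade 4 diarrhea that has resisted optimal therapy must then resolve within the one-week and day-28 limits, so the contrast in Step 3 is a best case.

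Investigators may stop treatment at any time (3.7, 3.11), and the DSMC oversees the trial (3.13). These are real safeguards, but none says whether re-exposure is allowed.

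The sentence making Grade 2 in the first cycle a DLT, placed inside the Grade 3 bullet, looks like an error but plausibly means still Grade 2 when the hold limit is reached. The first DLT criterion already covers that case, so it is only untidy wording.

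**Conclusion.** The contradiction is real and narrow. For an attributed Grade 4 non-hematologic event, the stop rule and the resume and day-21 rules cannot both be followed, and no precedence is stated. Under the four conditions in Step 2, the cost is up to two R-ICE cycles for a cycle 1 event and one for a cycle 2 event. The conclusion rests on reading the resume and day-21 text as covering attributed events, which nothing in it excludes.

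A reader might go further and infer a bias in the CR rate or damage to the two-stage design. The documents do not support that. They give no rate for such events. Patients who withdraw early still have CT and PET (Appendix 1 footnote i), and treated patients are not replaced (3.4.4). This is a matter of patient safety and uniform conduct across sites, and it should be fixed.

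The hold-limit mismatch is a smaller point of the same kind. The creatinine mismatch is separate. Section 4.1.5 sends eligibility to Section 3.3, so 7e-f governs and the footnote is the text in error; it should not be read as a second eligibility threshold.

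**What to change.** 1. In the Grade 4 bullet, state that it overrides the resume sentence, the day-21 list, the atrial fibrillation line, the DLT sentence on continuing, and the hepatic re-treatment sentence. If exceptions are intended (for example gastrointestinal, atrial fibrillation or hepatic events), list them in that bullet instead. Which of the two is right is a clinical decision for the lead investigator and sponsor; the text must carry one answer.
2. In the third bullet on non-hematologic toxicity, replace the day-28 condition with: *within 1 week of the date withheld and no later than Day 28 of the cycle*. In Section 3.11, replace the limit of more than 28 days with a reference to the hold and delay limits of Section 3.8.
3. Delete the Grade 2 sentence from the Grade 3 bullet, or reword it to match the first DLT criterion.
4. Align Appendix 1 footnote d with criterion 7e-f of Section 3.3.1: normal creatinine, or clearance of at least 40 if creatinine is raised.

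The cost is one wording amendment to Sections 3.8 and 3.11 and Appendix 1, with the IRB approval that Section 7.1 requires. Sample size, endpoints and scheduled procedures do not change.

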#### Cycle delay

After completion of each 21-day cycle, the start of a new cycle could be delayed for up to one 1 week (7 days) in cases of toxicity necessitating a dose delay. A subject whose cycle is delayed should be assessed within a week for resolution or recovery of toxicity and a decision regarding further delay.

There is no limit on the number of cycle delays that each subject may experience, as long as delays do not exceed one week or 28 days from the beginning of a cycle.

The following parameters must be met on the first day of a new cycle (after cycle 1):

- Platelet count  $\geq 50 \times 10^9/L$
- ANC  $\geq 1.0 \times 10^9/L$
- Non-hematologic toxicity of  $\geq$  grade 3 must have recovered to baseline or Grade  $\leq 1$

For severe hematologic toxicity (grade  $\geq 3$ ), laboratory evaluations may be repeated more frequently as necessary until the retreatment requirements are met. In the event of severe renal toxicity or hepatotoxicity, laboratory tests may be repeated more frequently as necessary until the toxicity resolves.

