#### Dose Limiting Toxicity: acalabrutinib + R-ICE

The DLT evaluation period begins with the first dose of acalabrutinib and ends immediately prior to the initiation of the second cycle. Only toxicities that occur during the DLT period will be used for the purposes of defining DLT. However, toxicities that occur in all cycles will be considered in the overall decisions of the investigators. The first 3-6 subjects will be evaluated for DLTs per above. Subjects considered non-evaluable for DLT may be replaced, but the safety profile of these subjects will be included in the investigator review. Subjects considered non-evaluable for DLT are subjects who do not complete Cycle 1 for reasons other than toxicity. Subjects who experience a DLT may continue treatment on the study at a lower dose of acalabrutinib.

The following will be considered DLTs after confirmation by the investigators:

- Complete treatment interruption of more than 7 days (28 days of the cycle) for acalabrutinib-RICE-related Grade  $\geq 2$  toxicities within Cycle 1

- Any Grade 3 or Grade 4 non-hematological toxicity that is at least possibly related to the study drugs
  - excluding:
    - Grade 3 nausea or vomiting responsive to anti-emetic treatment,
    - Grade 3 diarrhea responding to anti-diarrheal treatment,
    - Grade 3 fatigue/asthenia unless persisting for 7 days after stopping acalabrutinib and absent at baseline
    - alopecia
  - including:
    - persistent Grade  $\geq$  2 nausea and/or vomiting despite prolonged (more than 7 days continuously) anti-emetic treatment (5 HT3 antagonist, antihistamine, metoclopramide)
- Grade  $\geq$  2 hemorrhagic events requiring medical intervention
- Grade 4 hematological toxicity defined as:
  - Febrile neutropenia (ANC < 500 cells/ $\mu$ L with fever [body temperature  $\geq$  38.5°C] or sepsis) or Grade 4 neutropenia (ANC < 500 cells/ $\mu$ L) requiring at least 1 week delay of the next treatment cycle
  - Grade 4 thrombocytopenia (Platelet count < 25,000 cells/ $\mu$ L) requiring at least 1 week delay of next treatment cycle

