#### **3.11 WITHDRAWAL OF SUBJECTS FROM STUDY TREATMENT**

The investigator may withdraw any subject from study treatment, if, in the investigator's opinion, it is not in the subject's best interest to continue.

Any subject has the right to withdraw from the study at any time. In addition, subjects may be withdrawn from study treatment for the following reasons:

- Study treatment should be discontinued in the event of a toxicity lasting > 28 days as described in Section 3.8.
- Any subject who has **confirmed** objective evidence of cancer progression while receiving study treatment should be withdrawn from the study treatment. If there is uncertainty regarding whether there is true cancer progression, the subject may continue study treatment and remain under close observation (eg, evaluated at 4-week intervals) pending confirmation of progression.
- Any subject whose medical condition substantially changes after entering the study should be carefully evaluated by the investigator. Such subjects should be withdrawn from study treatment if continuing would place them at risk.
- Any subject who becomes pregnant or begins breastfeeding should be removed from study treatment.
- Any subject who becomes significantly noncompliant with study drug administration, study procedures, or study requirements should be withdrawn from study treatment in circumstances that increase risk or substantially compromise the interpretation of study results.

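### Section 3.8 gives opposite instructions for an acalabrutinib-related Grade 3 non-hematologic toxicity held before Day 21: stop if not recovered in 1 week, or restart if recovered by Day 28

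*Combined protocol and SAP*

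**What the plan says.** Four places in the protocol bear on when a patient with a held toxicity may restart.

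- **Section 3.8, dose-reduction paragraph** (after the list of DLTs). If an acalabrutinib-related event has not come down to an acceptable level, with Grade 1 or less given as the example for non-hematologic events, "within 1 week after the date acalabrutinib was withheld, treatment with acalabrutinib should be permanently discontinued". It adds that "the subject will be discontinued from the treatment" and that End-of-Treatment assessments follow.
- **Section 3.8, Non-hematological grade 3 or higher toxicities, first bullet.** For a Grade 3 event possibly or probably related to acalabrutinib, the whole regimen, R-ICE included, "is to be held for a maximum of 1 week (and d28 of a cycle) until the toxicity returns to Grade 1 or less".
- **Same list, third bullet.** "If Grade 3 toxicity returns to Grade 1 or less by Day 28, then proceed with next cycle of therapy", with acalabrutinib one dose level lower. No limit counted from the hold appears here.
- **Section 3.8, Cycle delay.** New cycles may be delayed "as long as delays do not exceed one week or 28 days from the beginning of a cycle". This shows where 28 comes from: a 21-day cycle plus 7 days.

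Section 3.11 then refers back: "Study treatment should be discontinued in the event of a toxicity lasting > 28 days as described in Section 3.8". The Study Synopsis has acalabrutinib taken on Days 1 to 21 of each of 3 cycles.

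**The concern.** One deadline runs from the date of the hold and the other from the start of the cycle. The third bullet neither repeats the 1-week limit nor defers to the paragraph that sets it, a Grade 4 bullet separates it from the first bullet, and no order of precedence is given.

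The sentence a site follows decides whether the patient leaves treatment or goes on to the next cycle at 100 mg daily. Following the third bullet as written re-exposes a patient whom the dose-reduction paragraph requires to be stopped. Section 3.8 itself says this combination has had no phase I study, which is why it has a safety lead-in. With three centers enrolling, the same clinical course could be handled differently from site to site.

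**Working it through.** The plan gives no figure to reproduce; the check is a count of days.

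**Inputs.** Acalabrutinib is dosed on Days 1 to 21 (Synopsis). The hold limit is 1 week from the date withheld (Section 3.8, dose-reduction paragraph). The third-bullet limit is Day 28 of the cycle (Section 3.8, non-hematologic list; origin in Cycle delay, 21 + 7 = 28).

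**Formulas.** Let the hold start on Day w, with w from 1 to 21.

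- 1-week deadline: Day w + 7.
- Third-bullet deadline: Day 28.
- Opposite instructions: recovery on Days w + 8 to 28.
- Length of that window: 28 − (w + 7) = 21 − w days.

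| Hold on Day | 1-week deadline | Recovery days in conflict | Length (days) |
|---|---|---|---|
| 1 | Day 8 | 9 to 28 | 20 |
| 7 | Day 14 | 15 to 28 | 14 |
| 14 | Day 21 | 22 to 28 | 7 |
| 20 | Day 27 | 28 | 1 |
| 21 | Day 28 | none | 0 |

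The window is positive for 20 of the 21 possible hold days and closes only at Day 21, so a hold before Day 21 is the exact condition.

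**Worked case.** Held on Day 7, still above the acceptable level on Day 14, Grade 1 on Day 18. Since 18 > 14, the dose-reduction paragraph stops the patient. Since 18 ≤ 28, the third bullet starts the next cycle.

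**Which limit is stricter.** The largest w + 7 is 21 + 7 = 28. For any hold on a dosing day the 1-week limit is never later than Day 28.

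**What one patient stands to receive or lose.** After a Cycle 1 event: 2 cycles × 21 days × 1 dose = 42 acalabrutinib doses at 100 mg daily, and 2 R-ICE courses. After a Cycle 2 event: 21 doses and 1 course. After a Cycle 3 event: none.

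**After the fix.** With the third-bullet deadline set to the earlier of w + 7 and 28, the window is 0 days for every w.

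**The case against.** The strongest reply is that the limits are cumulative. The first bullet covers the same event and caps the hold at 1 week; the third only states what to do on recovery. A patient already stopped permanently has no next cycle to start. A site that applies every sentence therefore reaches one answer, the stricter one. This reading is reasonable and shows which rule the fix should keep. But the protocol does not state it, and under it the third bullet's own deadline would never bind for a hold on a dosing day. A site can just as naturally take that deadline at face value.

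A second reply is that Section 3.8 thinks in terms of Day 21: it lists toxicities to be acted on at that day and pairs 1 week with Day 28 more than once. On that frame the deadlines coincide. It may explain how the mismatch arose, but the dose-reduction paragraph counts expressly from the date of withholding. If the investigators do intend Day 28 to govern, that is a clinical choice for them, and that paragraph and the first bullet would then have to change.

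Two stronger readings are tempting and are not supported.

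- **Section 3.11 as a third deadline.** A reader might add 28 days to a Day 7 hold and get Day 35. But that sentence defers to Section 3.8, where each 28 is a day of the cycle and not a duration of toxicity. It is a loose cross-reference.
- **The DLT definition as needing the same repair.** Its first item also pairs the two counts: "Complete treatment interruption of more than 7 days (28 days of the cycle". A reader might rewrite it to count Cycle 2 not started by Day 28. But nominal Cycle 2 Day 1 is Day 22, and a permitted 7-day delay ends on 22 + 7 = Day 29. The days missed, 22 to 28, number exactly 7, not more than 7. The rewrite would add a DLT trigger, and one DLT in the first 3 patients already lowers the dose for the next cohort.

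Investigator discretion to withdraw a patient, DSMC review of adverse events, and the separate interruption limit in Section 3.4.2 (whose unit reads days/weeks) do not settle which recovery deadline applies.

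**Conclusion.** The point holds as an inconsistency in the safety rules of Section 3.8. For a related Grade 3 non-hematologic toxicity held on Day w from 1 to 20, following the third bullet as written contradicts the dose-reduction paragraph whenever recovery falls on Days w + 8 to 28.

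The size is a span of calendar days, from 20 for a Day 1 hold to 1 for a Day 20 hold. A reader might take 20 of 21 hold days as a measure of risk. It is not one: the documents give no rate of such holds and no distribution of recovery times. Nor do they support an inferred effect on the lead-in, the CR rate or the error rates of the Simon design, and none is claimed.

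The day counts assume that the week ends on Day w + 7. The dose counts assume full dosing at 100 mg once daily. Counting R-ICE courses as lost assumes that being taken off the treatment covers the whole regimen; the End-of-Treatment assessments that follow favor that, but the sentence before it names only acalabrutinib.

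**What to change.** Keep the stricter limit, which the protocol already states twice.

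1. **Section 3.8, non-hematologic list, third bullet.** Reword to: *If the Grade 3 toxicity is Grade 1 or less within 1 week of the date of the acalabrutinib hold, and no later than Day 28 of the cycle, start the next cycle with acalabrutinib one dose level lower; otherwise discontinue as above.*
2. **Same list, first bullet.** State the limit as *a maximum of 1 week, and not beyond Day 28 of the cycle*. Leave its closing DLT sentence ("If grade 2 during the first cycle, this will be considered a DLT") as it is.
3. **Section 3.11.** Replace the reference to a toxicity of more than 28 days with *a toxicity not recovered within the limits in Section 3.8*. This corrects a cross-reference and sets no new deadline.

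Leave the DLT definition unchanged.

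The cost is a wording amendment to Sections 3.8 and 3.11, with no added patients, visits or procedures. The downside is that patients who recover after 1 week but by Day 28 do not restart, which the dose-reduction paragraph already requires.
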